**REVISION HISTORY**

*N/A*

Revision #	Version Date	Summary of Changes	Consent Change (Yes/No)

## 1. Study Summary

Peripheral Arterial Disease (PAD) refers to disorders characterized by progressive stenosis and altered structure and function of non-coronary arteries that supply the brain, visceral organs, and limbs. PAD is most commonly caused by atherosclerosis and plaque buildup.

Endarterectomy is a surgical intervention intended to address the narrowing or blockage of arteries caused by plaque buildup. Its goal is to enhance blood flow in affected areas and relieve associated symptoms. Various types of vascular patches are used during endarterectomies to reinforce vessel walls, repair arterial defects, reduce the risk of restenosis, and improve patient outcomes.

Postoperative surveillance, particularly through non-invasive ultrasound imaging, is essential for monitoring vascular patches' integrity and identifying potential complications. Ultrasound provides high-resolution visualization, enabling clinicians to detect abnormalities such as leaks or thrombosis early on. The non-invasive nature of ultrasound minimizes patient discomfort and allows for timely intervention, ultimately optimizing patient outcomes following vascular procedures.

VASCU-GUARD vascular patches by Baxter International Inc. are commonly used in the operating room. In November 2022, a package change has been made in the USA. Previously, each VASCU-GUARD patch was chemically sterilized and packaged in a jar filled with sterile, non-pyrogenic water containing propylene oxide. With the implementation of the new packaging, the patch is terminally sterilized via gamma irradiation and comes in a double-pouch system (where the contents of the outer pouch are sterile). The inner pouch maintains the bovine pericardium patch's moisture while packaged, and it doesn't contain any water or solution.

VASCU-GUARD vascular patches with the new packaging have been available at the Houston Methodist Hospital since January 2023. This study is a retrospective chart review, aiming to compare the performance of Baxter VASCU-GUARD vascular patches implemented during carotid endarterectomies (CEA) prior to January 2023 and after January 2023. This study is one of a kind, as no other comparative retrospective chart review on the performance of VASCU-GUARD vascular patches from the old and new packaging has been published yet.

The project will contribute to the scientific knowledge about long-term outcomes associated with the use of patch material during endarterectomies.

## 2. Purpose of the Study / Objectives

**PROTOCOL TITLE: *Ultrasound Evaluation for Baxter VASCU-GUARD Vascular Patches Post-Endarterectomy and Complications Assessment***

Primarily focusing on the implementation of VASCU-GUARD vascular patches in carotid endarterectomies (CEA), the study aims to identify VASCU-GUARD patches with old (before January 2023) and new (after January 2023) packaging and compare the results of standard-of-care exams between the two groups.

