### **3. Background**

Peripheral artery disease (PAD) results in the buildup of plaque in the arteries, leading to a disruption of blood flow to the head, organs, and limbs. In the US, it affects approximately 8.5 million people, predominantly those over the age of 40, and contributes significantly to healthcare costs, amounting to tens of billions of dollars annually.

Endarterectomy is a surgical procedure, during which atherosclerotic plaque from the inner lining of arteries is removed. The objective of endarterectomies is to improve blood flow in affected territories and to alleviate symptoms. The use of vascular patches in these interventions has become standard practice to reinforce vessel walls, repair arterial defects, reduce the risk of restenosis, and improve patient outcomes. Postoperative surveillance, especially through ultrasound imaging, plays a pivotal role in monitoring the efficacy of these vascular patches and identifying potential complications.

VASCU-GUARD vascular patches by Baxter International Inc. are commonly used in the operating room. In November 2022, a packaging change was made in the USA. Before November 2022, each VASCU-GUARD patch was chemically sterilized and packaged in a jar filled with sterile, non-pyrogenic water containing propylene oxide. With the new packaging, the patch is terminally

PROTOCOL TITLE: *Ultrasound Evaluation for Baxter VASCU-GUARD Vascular Patches Post-Endarterectomy and Complications Assessment*

sterilized via gamma irradiation and comes in a double-pouch system (where the contents of the outer pouch are sterile). The inner pouch maintains the bovine pericardium patch's moisture while packaged, and it doesn't contain any water or solution.

VASCU-GUARD vascular patches with the new packaging have been available at the Houston Methodist Hospital since January 2023. This study is a retrospective chart review aimed at comparing the performance of Baxter VASCU-GUARD vascular patches used in carotid endarterectomies (CEA) prior to January 2023 and after January 2023. This study is one of a kind, as no other comparative retrospective chart review on the performance of VASCU-GUARD vascular patches from the old and new packaging has been published yet.

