#### 4. Study Design

This study is a retrospective chart review. The data is collected from January the 1st 2022 till April the 30th 2024.

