##### *Medical Records Review*

Baseline information, operative information, and outcomes will be determined via retrospective review of medical records. Data obtained via medical record review will include demographic information (age, gender, ethnicity), baseline clinical information (medical co-morbidities, medications, history of underlying cause of peripheral artery disease, etc.) data on the operation (date of operation/procedure, discharge date, surgeons name, anatomical site, campus where the surgery was performed, type of anesthesia, intraoperative blood pressures, estimated blood loss, intraoperative complications, etc.), results of standard-of-care exams.

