##### *Statistical Analysis*

A retrospective chart review will be conducted on a maximum of 500 patients. Analyzing data from 500 patients will provide a robust baseline to conduct a study of differences, similarities, and trends among the patients. All information will be entered into an electronic excel database created for the study and analyzed in STATA statistical program. All subjects meeting eligibility criteria will be enrolled.

The data will be abstracted from Houston Methodist Hospital electronic medical records, DigiView and from the MCVSA office charts by the PI and trained members of his research staff. The required information will be transferred from electronic medical records by the research staff to the study specific electronic Excel data collection forms.

**PROTOCOL TITLE: *Ultrasound Evaluation for Baxter VASCU-GUARD Vascular Patches Post-Endarterectomy and Complications Assessment***

Permission to review medical records will be obtained from the Houston Methodist Hospital Research Institute (TMHRI) Human Subjects Committee via a HIPAA Waiver of Authorization and Waiver of Consent.

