**Data to be collected:**

- Age at surgery, sex, race
- Preoperative risk factors: HTN, DM, TIA, CAD, HLD, previous strokes, previous thromboembolic events, previous surgeries
- Intraoperative data: Type of patch material used, intraoperative complications (if any), MAP, Heart rate, Medications given, Estimated blood loss, Intraoperative antibiotics given, Intraoperative antiplatelet/anticoagulation medication given
- Postoperative outcomes: Stroke/TIA, Postop ICU time, mortality (up to 30 days)
- Follow up neurological evaluation, any symptoms reported by the patient
- Imaging: MRI/CT, MRA, CTA, TCD, vascular duplex ultrasound

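### Packaging group is assigned by a calendar date around January 2023, and no listed data field would show an old-packaging patch used after it

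*Protocol*

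**What the plan says.** The exposure is a product difference. Section 1 of the Protocol describes the earlier patch as chemically sterilised and stored in fluid in a jar, and says of the later one: "With the implementation of the new packaging, the patch is terminally sterilized via gamma irradiation and comes in a double-pouch system". Section 2 sets the aim to "identify VASCU-GUARD patches with old (before January 2023) and new (after January 2023) packaging" and to compare standard-of-care results between the two groups. Sections 1 and 3 restate the comparison by time alone, as patches used "prior to January 2023 and after January 2023".

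The basis for the cut-off is local supply: "VASCU-GUARD vascular patches with the new packaging have been available at the Houston Methodist Hospital since January 2023". The packaging change in the USA is dated November 2022. Section 10 covers all campuses of the hospital and requires only that a VASCU-GUARD patch was used.

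The fields to be abstracted are listed in section 4. The operative items under Medical Records Review include operation date and campus, and the list ends open: "estimated blood loss, intraoperative complications, etc". The data list has one patch item: "Intraoperative data: Type of patch material used, intraoperative complications (if any". The ultrasound list describes the implanted patch and the blood flow. None of these lists names packaging, lot, catalogue number or expiry date.

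**The concern.** Calendar date stands in for the exposure, and the stated reason for the date supports only one side of it. If the new version was not available at the hospital before January 2023, earlier operations can be taken as old. Availability from that month does not show that every later operation used the new version. Hospitals can run down stock, and several campuses may not switch on the same day.

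Any misplacement therefore runs one way: old patches counted as new. If those patients carry the old group's risk, the two groups are pulled together. A finding of little or no difference is a plausible and important result when a product's sterilisation has changed. It would be partly open to this explanation, and nothing in the listed data could say how much. An analysis plan cannot repair this later if the identifying field was never abstracted.

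A smaller wording point: groups before and after January 2023 leave that month in neither, although the statement on availability suggests it is meant as new.

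**Working it through.** The Protocol gives no figure for misclassification, so there is none to reproduce. The check has two parts.

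**1. Could any stated field reveal an old patch used after the cut-off?**

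- *Operation date and campus* (section 4, Medical Records Review): these are the proxy itself and cannot contradict it.
- *Type of patch material* (section 4, data list): every eligible patient has VASCU-GUARD, and the described change is to sterilisation and container. As worded, this item does not separate the groups.
- *Ultrasound items* (section 4): these are outcomes, not product identity.
- *Recorded identifiers* (section 8 table): names, dates and medical record numbers only.
- *Section 18 identifier checklist*: it contains a line for device identifiers, but the available text does not show whether it was ticked.

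No stated field does the job. Two openings remain: the open-ended operative list and the checklist line.

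**2. How much would mixing matter?**

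Inputs from the Protocol: the data window (section 4: "The data is collected from January the 1" of the month, 2022, to 30 April 2024) and the ceiling on sample size ("A retrospective chart review will be conducted on a maximum of 500 patients").

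Assumptions: m, the share of the date-defined new group that was old stock, is unknown and may be zero. Misplaced patients carry the old group's risk. Accrual is uniform over the window, used only to turn shares into patient counts.

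*Days.* 365 + 365 + 121 = 851 in total. From 1 January 2023: 365 + 121 = 486. Expected new group: 486/851 × 500 = 285.5, about 286.

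*Dilution.* The risk observed in the new group is m × p_old + (1-m) × p_new. Subtracting p_old leaves (1-m) × (p_new - p_old). With roughly unchanged variance, the information kept is about (1-m)², so the comparison behaves like one of (1-m)² × 500 correctly classified patients.

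| m | Misplaced patients (m × 286) | Share of difference kept (1-m) | Equivalent of 500 |
|---|---|---|---|
| 0% | 0 | 1.00 | 500 |
| 2% | 5.7 | 0.98 | 0.9604 × 500 = 480 |
| 5% | 14.3 | 0.95 | 0.9025 × 500 = 451 |
| 10% | 28.6 | 0.90 | 0.81 × 500 = 405 |

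To put m in terms of time: if old stock had supplied every operation in January 2023, with that month counted as new, m would be 31/486 = 6.4%.

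*January wording.* 31/851 = 3.6% of the window, or about 18 of 500 patients under uniform accrual.

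**The case against.** The strongest reply is that section 2 makes packaging the thing to be identified. The bracketed dates may only describe when each version was in use, and the abstractors may well look at the implant record. The study's data forms are not shown, the operative list is open-ended, and the device-identifier line may have been ticked. No passage shows that an old patch was used after the cut-off. Over the range of m considered, at least 90% of the difference survives, and the Protocol states no power or effect size for the dilution to break. The 500 is a ceiling for chart review, not a powered sample size. A changeover-period exclusion could also be run from operation date and campus, which are already listed.

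Much of this stands as a limit on the size of the problem. The harm is possible, not shown, and modest at small m. The equivalent patient numbers are only a scale. It does not remove the point. Sections 1 and 3 phrase the comparison purely by date, and no passage states another criterion or a field to support one. A date-based exclusion helps only if the length of the run-down is known, and without a packaging field it is not.

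Section 8 says that identifiers will not enter the cohort analysis, which might seem to bar grouping by lot number. The same sentence would bar grouping by operation date, which the plan already does. A plain packaging-type field avoids the question.

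**Conclusion.** The concern holds. The Protocol assigns a product exposure by a date that is justified on one side only, and lists no field that would expose an error on the other. The loss is the fraction m of the true difference: nil if no old stock was used after the cut-off, 2% to 10% for m between 2% and 10%. At the 500-patient ceiling this is like comparing 480 to 405 correctly classified patients. These sizes rest on an assumed m and on misplaced patients carrying the old group's risk. The patient counts also assume uniform accrual. This should be changed, but it does not by itself undermine the study. Confidence is medium, because a packaging field may be collected without being named. The January 2023 gap is a wording fault affecting 3.6% of the window.

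**What to change.** 1. Add packaging type, or catalogue or lot number, taken from the implant record, to the data list in section 4. State that the group is assigned from it.
2. Where it is missing, assign by an explicit boundary: before 1 January 2023 is old, on or after 1 January 2023 is new. This also settles January. Flag these patients as date-assigned.
3. Report the number of date-assigned patients in each group, and repeat the comparison without those from the changeover months.

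The cost is one more field from operative records already being opened and a short wording change in sections 1 to 3. If lot or serial numbers are used instead of packaging type, the section 8 table may need a further row and its sentence on identifiers a clarification. Some charts may lack the information, so part of the cohort may stay date-assigned. If the field shows no mixing, the comparison gains a verified exposure.

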**The objectives of this study include:**

*Ultrasound evaluation of Baxter VASCU-GUARD vascular patches:*

Retrospective review of ultrasound recordings and ultrasound reports at one-month, 3-months, 6-months and 1-year follow-up after endarterectomy – if available, to evaluate patch patency, morphology, integrity, complications, and blood flow dynamics.

*Complications assessment:*

Analyze complications linked with Baxter Vascular Patches (VASCU-GUARD), including but not limited to thrombosis, stroke, dissection, restenosis, infection, fluid collection, pseudoaneurysm formation, fraying or irregularities in patch material.

*Correlation with Clinical Outcomes:*

Recognize correlations between ultrasound findings and clinical outcomes. This correlation will complement the understanding of how ultrasound monitoring can predict and influence patient prognosis.

### **3. Background**

Peripheral artery disease (PAD) results in the buildup of plaque in the arteries, leading to a disruption of blood flow to the head, organs, and limbs. In the US, it affects approximately 8.5 million people, predominantly those over the age of 40, and contributes significantly to healthcare costs, amounting to tens of billions of dollars annually.

Endarterectomy is a surgical procedure, during which atherosclerotic plaque from the inner lining of arteries is removed. The objective of endarterectomies is to improve blood flow in affected territories and to alleviate symptoms. The use of vascular patches in these interventions has become standard practice to reinforce vessel walls, repair arterial defects, reduce the risk of restenosis, and improve patient outcomes. Postoperative surveillance, especially through ultrasound imaging, plays a pivotal role in monitoring the efficacy of these vascular patches and identifying potential complications.

VASCU-GUARD vascular patches by Baxter International Inc. are commonly used in the operating room. In November 2022, a packaging change was made in the USA. Before November 2022, each VASCU-GUARD patch was chemically sterilized and packaged in a jar filled with sterile, non-pyrogenic water containing propylene oxide. With the new packaging, the patch is terminally

PROTOCOL TITLE: *Ultrasound Evaluation for Baxter VASCU-GUARD Vascular Patches Post-Endarterectomy and Complications Assessment*

sterilized via gamma irradiation and comes in a double-pouch system (where the contents of the outer pouch are sterile). The inner pouch maintains the bovine pericardium patch's moisture while packaged, and it doesn't contain any water or solution.

VASCU-GUARD vascular patches with the new packaging have been available at the Houston Methodist Hospital since January 2023. This study is a retrospective chart review aimed at comparing the performance of Baxter VASCU-GUARD vascular patches used in carotid endarterectomies (CEA) prior to January 2023 and after January 2023. This study is one of a kind, as no other comparative retrospective chart review on the performance of VASCU-GUARD vascular patches from the old and new packaging has been published yet.

Ultrasound provides high-resolution visualization, enabling clinicians to detect abnormalities such as leaks or thrombosis early on. The non-invasive nature of ultrasound minimizes patient discomfort and allows for timely intervention, ultimately optimizing patient outcomes following vascular procedures.

[figure not shown]

Figure 1. Ultrasound showing pseudoaneurysm formation directly from the patch material. Left – true lumen is measured with yellow crosses. Right – “Pepsi sign” on color Doppler in the context of bidirectional flow from a pseudoaneurysm.

**PROTOCOL TITLE: *Ultrasound Evaluation for Baxter VASCU-GUARD Vascular Patches Post-Endarterectomy and Complications Assessment***

[figure not shown]

Figure 2. Ultrasound showing irregularities in the patch material due to infection.

#### 4. Study Design

This study is a retrospective chart review. The data is collected from January the 1st 2022 till April the 30th 2024.

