**Postoperative ultrasound follow-up:**

- ultrasound assessment of the vascular patch: patch patency, morphology, integrity, complications, and blood flow dynamics.
- detection of complication: thrombosis, dissection, restenosis, infection, fluid collection, pseudoaneurysm formation, fraying or irregularities in patch material
- repeat ultrasound assessment: morphological changes in the vascular patch, evolution of blood flow dynamics, signs of restenosis or complications
- Data obtained from duplex ultrasound: wall thickness, presence of plaque, lumen diameter, peak systolic velocity (PSV), end-diastolic velocity (EDV), mean flow velocity (MFV), pulsatility index (PI), direction of blood flow, velocities, degree of stenosis

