**18. Waiver of Informed Consent and /or Authorization**

Requesting a waiver of informed consent and HIPAA waiver of authorization.

We are requesting a waiver of authorization for the conduct of this research study. As this project only involves the analysis of secondary data in the patient chart, it is deemed minimal risk for participants, and therefore, a waiver of consent can apply. All data being collected are

PROTOCOL TITLE: *Ultrasound Evaluation for Baxter VASCU-GUARD Vascular Patches Post-Endarterectomy and Complications Assessment*

part of the standard of care, and thus, a waiver should apply as the data being collected is used to understand underlying factors that affect the variables being collected.

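### Section 4 gives one data window without separating surgery dates from a follow-up cut-off; if it caps follow-up, about a quarter of new-packaging patients but all old-packaging patients could reach the 1-year ultrasound

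*Protocol*

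**What the plan says.** The only study dates in the protocol are in Section 4: "The data is collected from January the 1 st 2022 till April the 30 th 2024". No section gives a surgery window and a follow-up cut-off as separate dates.

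Section 2 aims to "identify VASCU-GUARD patches with old (before January 2023) and new (after January 2023) packaging" and to compare the two groups. Section 3 gives the site date for the change: "VASCU-GUARD vascular patches with the new packaging have been available at the Houston Methodist Hospital since January 2023".

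The first objective in Section 2 covers recordings and "ultrasound reports at one-month, 3-months, 6-months and 1-year follow-up after endarterectomy – if available". The follow-up list in Section 4 adds "detection of complication: thrombosis, dissection, restenosis, infection, fluid collection, pseudoaneurysm formation, fraying or irregularities in patch material", with no time horizon of its own.

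Section 10 requires that some follow-up ultrasound exists and sets no minimum length of follow-up. The Statistical Analysis part of Section 4 says "A retrospective chart review will be conducted on a maximum of 500 patients" and gives no split by group. Section 1 says that the project will "contribute to the scientific knowledge about long-term outcomes associated with the use of patch material during endarterectomies".

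**The concern.** The two groups occupy consecutive calendar periods, so a common end date gives the later group less follow-up. Follow-up scans are data. A window on data collection, read plainly, therefore ends follow-up on 30 April 2024 for everyone, and the shortfall falls on the new packaging only.

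Two things are at stake. First, the 1-year comparison would rest on new-packaging patients operated in about the first four months of use, and no later analysis can recover 1-year scans that the window excludes. Second, the groups would have unequal time at risk for complications. If complications were counted without regard to follow-up time, the new packaging could look better for that reason alone.

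The qualifier that closes the first objective tolerates a missing scan in any patient. It does not deal with a calendar limit that affects one comparison group and spares the other.

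**Working it through.** The protocol states no power, precision or share of patients reaching 1 year, so it has no figure to reproduce. The check is calendar arithmetic.

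**Inputs.** Window 1 January 2022 to 30 April 2024 (Section 4); split at January 2023 (Sections 2 and 3), taken as 1 January because no day is given; visits at 1, 3, 6 and 12 months (Section 2); maximum 500 patients (Section 4). Assumptions: the window caps both surgery and follow-up, groups are assigned by date, and accrual is even. The protocol gives no surgical volumes.

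**Possible follow-up.**
- Old packaging: surgery 1 January to 31 December 2022, 365 days. Time to 30 April 2024: 486-850 days.
- New packaging: surgery 1 January 2023 to 30 April 2024, 486 days. Time to 30 April 2024: 0-485 days.

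**Share able to reach each visit** = surgery days at least that long before 30 April 2024 / all surgery days in the group.

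| Visit | New packaging | Old packaging |
|---|---|---|
| 1 month | 455/486 = 94% | 100% |
| 3 months | 395/486 = 81% | 100% |
| 6 months | 303/486 = 62% | 100% |
| 12 months | 120/486 = 25% | 100% |

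With 1 year taken as 365 days, the last figure is 121/486, also 25%. These are possible scans, not scans actually done.

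**Effect of the scan requirement in Section 10.** Patients operated too late to have had any scan do not enter the cohort, so the denominator shrinks. First scan at about 1 month: 120/455 = 26%. First scan at about 3 months: 120/395 = 30%. Earlier first scans move the share back towards 25%.

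**Other assumptions, new-packaging share at 1 year.**
- Counting from 1 February 2023: 89/455 = 20%.
- Daily surgery rate doubling or halving linearly over the 851 days: 22% or 29%.
- New stock phased in linearly over 90 or 181 days: 17% or 10%.
- A scan from 11 or 10 months accepted as the 1-year visit: 151/486 = 31% or 181/486 = 37%.

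The range is roughly 10-37%. The old group stays at 100% as long as groups are assigned by date.

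**Numbers at the 500-patient maximum (base case).**
- Old: 500 × 365/851 = 214. New: 500 × 486/851 = 286.
- New and able to reach 1 year: 286 × 121/486 = 71.
- With the scan requirement, first scan at 1 month: 500 × 365/820 = 223 vs 500 × 120/820 = 73. At 3 months: 500 × 365/760 = 240 vs 500 × 120/760 = 79.
- With the linear accrual trends the old group is 174 (doubling) or 255 (halving), and the new group able to reach 1 year stays at about 71.

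**Precision of a difference in risk.** 95% half-width = 1.96 × √[p(1−p)(1/n₁ + 1/n₂)], with p an assumed common risk.

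| p | 214 vs 71 | 214 vs 286 |
|---|---|---|
| 5% | 5.9 points | 3.9 points |
| 10% | 8.1 points | 5.3 points |
| 15% | 9.6 points | 6.3 points |

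If only 80% of possible scans exist in both groups, the figures at 10% risk are 9.0 points (171 vs 57) against 5.9 (171 vs 229).

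**The case against.** The strongest objection is that the protocol does not say that the window caps follow-up. The sentence could describe surgery dates, with charts read beyond April 2024. That stands: every figure above is conditional. On that reading no imbalance is shown, and what remains is that no follow-up cut-off is stated, so abstractors could stop at different dates under the same protocol.

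Several stronger readings are tempting and should not be drawn.

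- A reader might infer that the comparison of complications is biased towards the new packaging. The protocol does not commit to a count that ignores follow-up time, so this is only a possibility. At visits anchored to time since surgery, the effect is mainly lost precision.
- A reader might take the 1-year visit as the principal one because Section 1 speaks of long-term outcomes. Section 2 lists four visits without ranking them, several listed complications can occur early, and mortality is collected only to 30 days. Outcomes within 30 days are hardly affected.
- A reader might treat 214 vs 71 as a ceiling. It is a base case: a falling surgery rate gives 255 in the old group, and the scan requirement shifts both numbers.

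It is also fair to say that the risks, accrual patterns and scan availability are assumptions, and that a wider interval contradicts no stated target. Censoring rules belong in a statistical analysis plan, which is not at hand. The data window does not: the protocol itself fixes it as part of the design.

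**Conclusion.** The concern holds in conditional form. It is certain that Section 4 gives one window and does not separate surgery from follow-up. If that window caps follow-up, the 1-year ultrasound is open to all old-packaging patients and to about 25% of new-packaging patients under even accrual, about 26-30% once a first scan at 1-3 months is required, and roughly 10-37% across the other assumptions. None of these comes near the old group's share.

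The consequence is a 1-year comparison about half as imprecise again as it could be (8.1/5.3 = 1.5 at an assumed 10% risk) and drawn from the earliest new-packaging patients, plus a potential distortion in complication counts if time at risk is ignored. This should be corrected. Confidence is medium, because the size depends on a reading that the protocol does not spell out.

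**What to change.** In Section 4, state the surgery window and the follow-up cut-off as two dates.

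**Preferred.** Keep 30 April 2024 as the last surgery date and set the chart cut-off up to 12 months later. With 365 days needed, the new-packaging share able to reach 1 year would be 305/486 = 63% for a cut-off of 31 October 2024, 397/486 = 82% for 31 January 2025, and 100% for 30 April 2025. The cost is a later data cut. The waiver request in Section 18 is argued on the ground that "As this project only involves the analysis of secondary data in the patient chart" and on retrospective, clinically available data, so the waivers must be confirmed, or amended, to cover the added records. No patient procedure changes.

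**Otherwise.** Keep 30 April 2024 for both, limit the 1-year comparison to patients operated at least 12 months earlier, state the smaller new-packaging sample, and say that complications are compared over the same time since surgery in both groups. The detailed censoring rules can be left to the statistical analysis plan. The cost is the wording and an openly smaller 1-year sample.
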